**Statistical Analysis:**

Approximately 300 patients will be randomized at a 1:1:1 ratio in the Blinded Treatment Dosing Period to ixekizumab 80 mg Q2W, ixekizumab 80 mg Q4W, and placebo. With 100 patients per treatment group, this study will have approximately 96% power to test the superiority of ixekizumab Q2W to placebo for the ASAS40 at Week 16. The following assumptions were used for the power calculations for ASAS40 response rates at Week 16 regardless of ixekizumab starting dose: 27% for ixekizumab Q2W treatment group and 7% for placebo group. A 2-sided Fisher's exact test at the 0.05 level is assumed. The efficacy analyses for the Blinded Treatment Dosing Period will be conducted on the intent-to-treat (ITT) population, and safety analyses will be conducted on the safety population.

Comparisons between each ixekizumab treatment group (80 mg Q2W or 80 mg Q4W) and placebo will be performed for all analyses in the Blinded Treatment Dosing Period. Unless otherwise specified, ixekizumab 80 mg Q2W and Q4W groups will be analyzed without regard to starting dose. The primary analysis method for treatment group comparisons of categorical efficacy and health outcomes variables will be a logistic regression analysis with treatment, geographic region, baseline CRP status (nonelevated or elevated), and prior number of TNF inhibitor used (1 or 2) as factors, using the nonresponder imputation (NRI) method. Under NRI, all nonresponders at Week

16 (Visit 8), as well as all patients who discontinue study treatment at any time prior to Week 16 for any reason, will be defined as nonresponders for the NRI analysis at Week 16. Randomized patients without any postbaseline observation will also be defined as nonresponders for the NRI analysis. A graphical multiple testing strategy for the primary and major secondary objectives will be implemented to control the family-wise type I error rate at a 2-sided  $\alpha$  level of 0.05.

The primary analyses for the continuous efficacy and health outcomes variables will be made using mixed-effects model of repeated measures (MMRM) analysis with treatment, geographic region, baseline CRP status, prior number of TNF inhibitor used, baseline value, visit, baseline value-by-visit, and treatment-by-visit as fixed factors.

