
 • To determine if the effect of either ixekizumab regimen is maintained through Week 52 • To explore effect of starting dose (160 mg compared to 80 mg) • To evaluate the incidence of anti-ixekizumab antibodies and their relationship to the efficacy of ixekizumab • To measure ixekizumab exposure and assess the relationship between exposure and efficacy, and exposure and immunogenicity 	
All endpoints assessed at Week 16 (above) and during the 16-week placebo-controlled period (above) will continue to be assessed through Week 52 (with the exception of MRI-related endpoints).
 
In addition, the following endpoint is added:
 
 • NSAID intake (ASAS-NSAID score and % of patients taking NSAIDs) • Onset of action and treatment response (ASAS and CRP) during the placebo-controlled period • Efficacy response rates listed below at Weeks 16 and 52 by treatment-emergent anti-drug antibody (TE-ADA) status and by neutralizing anti-drug antibody (NAb) status: 
 ○ Proportion of patients achieving ASAS40 ○ Proportion of patients achieving ASAS20 ○ Proportion of patients achieving ASDAS <2.1 • Serum trough concentrations of ixekizumab • Model parameters for the exposure-response relationship between ixekizumab serum trough concentrations and efficacy endpoints (for example, ASAS20, ASAS40) at Weeks 16 and/or 52 • Ixekizumab serum trough concentrations associated

Abbreviations: CRP = C-reactive protein; DNA – deoxyribonucleic acid; mRNA = messenger ribonucleic acid; NSAID = nonsteroidal anti-inflammatory drug; Q2W = every 2 weeks; Q4W = every 4 weeks; TE-ADA = treatment-emergent anti-drug antibody.

5. Study Design

[figure not shown]
This section contains the summary of study design, the method of treatment assignment, and the sample size determination from the protocol for Study I1F-MC-RHBW (RHBW).

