6.1. General Considerations

Statistical analysis of this study will be the responsibility of Eli Lilly and Company (Lilly). The statistical analyses will be performed using SAS® Version 9.2 or higher.

Continuous data will be summarized in terms of the number of observations, mean, standard deviation (SD), minimum, median, and maximum. The minimum and maximum will be reported to the same number of decimal places as the raw data recorded in the database. The mean and median will be reported to 1 more decimal place than the raw data recorded in the database. The SD will be reported to 2 more decimal places than the raw data recorded in the database. In general, the maximum number of decimal places reported shall be 4 for any summary statistic.

Categorical data will be summarized in terms of the number of patients in the analysis population, the number of patients providing data at the relevant time point, frequency counts, and the percentages corresponding to the appropriate method. Percentages will be presented to 1 decimal place. Percentages will not be presented for zero counts.

All confidence intervals (CIs) and statistical tests will be 2-sided unless otherwise specified. P-values which are ≥ 0.001 , and ≤ 0.999 , will be presented to 3 decimal places. All other p-values which are < 0.001 will be presented as < 0.001 , while p-values greater than 0.999 will be presented as > 0.999 . Confidence intervals (CIs) will be presented to 1 more decimal place than the raw data.

Age, sex, and race will be reported on all by-patient listings unless otherwise specified. Sex will be abbreviated as follows: female (F) and male (M). Race will be abbreviated as follows: American Indian or Alaska Native (AI), Asian (AS), Black or African American (BL), Native Hawaiian or other Pacific Islander (NH), White (WH), and Multiple (MU).

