Selective efficacy and health outcomes analyses will be performed for Combined Periods 2 and 3 for the ITT population who are randomized to ixekizumab at Week 0 (Visit 2). These analyses include the primary endpoint, all major secondary endpoints, as well as BASDAI50, ASDAS inactive disease, ASDAS clinically important improvement and major improvement.

Unless otherwise specified, Combined Periods 2 and 3 starts at the first injection of study treatment at Week 0 (Visit 2) and ends on the date of Week 52 (Visit 15) or the ETV (between Weeks 0 and 52).

For the efficacy and health outcomes analyses, baseline is defined as the last available value before the first injection in Period 2 and, in most cases, will be the value recorded at Week 0 (Visit 2). For efficacy measures, if the patient does not take any injection, the last available value on or before randomization date will be used.

The number and percentage of patients achieving a categorical response (for example, ASAS40) will be summarized by treatment group for all scheduled visits (NRI), including Week 52 (Visit 15).

Continuous measure score and change from baseline will be summarized by treatment group at all scheduled visits, including Week 52 (Visit 15) using descriptive statistics (n, mean, SD, median, minimum, and maximum). Missing data will be imputed using mBOCF method (Section 6.3.2).

Selected safety analyses will be performed for Combined Periods 2 and 3 for the Safety Population who are randomized to ixekizumab at Week 0 (Visit 2).

For the above safety analyses, baseline will be defined as the last available value before the first injection at Week 0. In most cases, this will be the measure recorded at Week 0 (Visit 2). For TEAEs, baseline is defined as the time from Visit 1 to the date/time of the first injection.

Additional categorical safety analyses will be conducted in the All Ixekizumab Exposures Safety Population (defined in Section 6.1.5), for each patient, and will include only periods in which ixekizumab is administered. Exposure-adjusted incidence rates of AEs during Week 0-52 timeframe will be provided. For these safety analyses, baseline is defined as follows:

- If ixekizumab is dispensed at Week 0, baseline will be defined as the last available value before the first injection at Week 0. In most cases, this will be the measure recorded at Week 0 (Visit 2). For TEAEs, baseline is defined as the time from Visit 1 to the date/time of the first injection.

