6.1.5. Analysis Populations

The following major analysis populations will be used (additional analysis populations for specific analysis will be defined in the corresponding analysis section):

Intent-to-Treat Population (ITT Population): Unless otherwise specified, efficacy and health outcomes analyses for Period 2 will be conducted on the ITT Population, defined as all randomized patients, even if the patient does not take the assigned treatment, does not receive the correct treatment, or otherwise does not follow the protocol. Patients will be analyzed according to the treatment to which they were assigned.

Per-Protocol Set (PPS): In addition, the primary efficacy analysis will be repeated using the PPS, which is defined as all randomized patients who do not have a subset of important protocol deviations that impact the primary efficacy endpoint (Section 6.14). For example, patients who are not compliant with therapy during the double-blind period will be excluded from the PPS. Compliance with therapy is defined to be missing no more than 20% of expected doses, not missing 2 consecutive doses (all injections in an injection week are counted as 1 dose), and not have any occurrence of over-dosing (that is, took more injections at the same time point than specified in the protocol) during Period 2.

Patients will be analyzed according to the treatment to which they were assigned.

Safety Population: Safety analyses for Period 2 will be conducted on the Safety Population, defined as all randomized patients who received at least 1 dose of study treatment. Patients will be analyzed according to the treatment to which they were assigned in that period.

Extended Treatment Period Population: Efficacy, health outcomes, and safety analyses for Period 3 will be conducted on the Extended Treatment Period Population, defined as all patients who received at least 1 dose of ixekizumab treatment during Period 3.

All Ixekizumab Exposures Safety Population: Safety analyses for combined Blinded Treatment Dosing Period and Extended Treatment Period will be conducted on the All Ixekizumab Exposures Safety Population, defined as all patients who received at least 1 dose of ixekizumab during the study. For each patient, only periods in which ixekizumab is administered are included.

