		ANCOVA with mBOCF/LOCF	ITT Population	IXE80Q2W & IXE80Q4W vs. placebo at Week 16	Other secondary efficacy analyses (Section 6.10.4)
ASSpiMRI-Berlin Score	ASSpiMRI Berlin change from baseline	ANCOVA with observed case analysis	ITT Population who participate in MRI addendum	IXE80Q2W & IXE80Q4W vs. placebo at Week 16	Other secondary efficacy analyses (Section 6.10.2)
		ANCOVA with mBOCF	ITT Population who participate in MRI addendum	IXE80Q2W & IXE80Q4W vs. placebo at Week 16	Other secondary efficacy analyses (Section 6.10.4)
ASAS	ASAS5/6 and ASAS partial remission	Logistic regression analysis with NRI; Fisher's exact test with NRI	ITT Population	IXE80Q2W & IXE80Q4W vs. placebo at Week 16 and all other postbaseline visits in Period 2	Other secondary efficacy analyses (Section 6.10.4)
		Descriptive statistics of ASAS5/6 response rate and ASAS partial remission	Extended Treatment Period Population	No treatment group comparisons during Period 3	Other secondary efficacy analyses (Section 6.10.4) This summary includes Extended Treatment Period Population overall and by ASAS20 or ASAS40 response status (responder vs. nonresponder) at Week 16 (Visit 8) (NRI)

Measure	Variable	Analysis Method (Sections 6.1, 6.3)	Population (Section 6.1.5)	Comparison/Time Point	Analysis Type
Patient Global	Patient Global change and % improvement from baseline	MMRM	ITT Population	IXE80Q2W & IXE80Q4W vs. placebo at Week 16 and all other postbaseline visits in Period 2	Other secondary efficacy analyses (Section 6.10.4)
		ANCOVA with mBOCF	ITT Population	IXE80Q2W & IXE80Q4W vs. placebo at Week 16 and all other postbaseline visits in Period 2	Other secondary efficacy analyses (Section 6.10.4)
		Descriptive statistics of change from baseline	Extended Treatment Period Population	No treatment group comparisons during Period 3	Other secondary efficacy analyses (Section 6.10.4)
Spinal Pain	Spinal Pain and Spinal Pain at night change and % improvement from baseline	MMRM	ITT Population	IXE80Q2W & IXE80Q4W vs. placebo at Week 16 and all other postbaseline visits in Period 2	Other secondary efficacy analyses (Section 6.10.4)
		ANCOVA with mBOCF	ITT Population	IXE80Q2W & IXE80Q4W vs. placebo at Week 16 and all other postbaseline visits in Period 2	Other secondary efficacy analyses (Section 6.10.4)
		Descriptive statistics of change from baseline	Extended Treatment Period Population	No treatment group comparisons during Period 3	Other secondary efficacy analyses (Section 6.10.4)

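### Secondary and health-outcome endpoints outside the SAP 6.1.3 list change denominator between Week 16 (all randomized) and Week 52 (only patients dosed in Period 3), so maintenance is not read like for like

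*SAP*

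**What the plan says.** SAP Section 4 makes it an objective to find out whether the effect of either regimen lasts to Week 52. Its scope is broad: the Week 16 and placebo-controlled-period endpoints "will continue to be assessed through Week 52 (with the exception of MRI-related endpoints".

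Three populations then matter (SAP Sections 6.1.3 and 6.1.5, Tables RHBW.6.1 and 6.2):

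- **Period 2, including Week 16:** ITT, meaning everyone randomized.
- **Period 3:** "Efficacy, health outcomes, and safety analyses for Period 3 will be conducted on the Extended Treatment Period Population", which requires an ixekizumab dose in Period 3.
- **Combined Periods 2 and 3:** ITT patients randomized to ixekizumab at Week 0, with nonresponder imputation (NRI) or modified baseline observation carried forward (mBOCF), at all scheduled visits to Week 52.

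The third population is the like-for-like one, and Section 6.1.3 limits its efficacy use: "These analyses include the primary endpoint, all major secondary endpoints, as well as BASDAI50, ASDAS inactive disease, ASDAS clinically important improvement and major improvement". Table RHBW.6.5 adds a combined-period row for anterior uveitis. For other measures, Tables RHBW.6.5 and 6.7 have an ITT row for Period 2 and an Extended Treatment Period Population row for Period 3, with no combined row. The Period 3 row labelled "Descriptive statistics of ASAS5/6 response rate and ASAS partial remission" is an example.

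Section 6.10.4 says that Period 3 and combined-period efficacy is descriptive, without inferential testing.

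**The concern.** To judge whether, say, partial remission is maintained, a reader has to set a Week 16 percentage of all randomized patients against a Week 52 percentage of those who went on to be dosed in Period 3. A patient who stops before Week 16 counts as a failure at Week 16 and is absent afterwards. The denominator shrinks and the numerator does not, so the rate can rise, or stay flat while responders are lost, for a reason unrelated to maintenance.

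The measures in this position are ASAS5/6, ASAS partial remission, MASES = 0 and SPARCC enthesitis = 0, TJC = 0 and SJC = 0, the two ASAS HI responder measures, the 50% decrease in QIDS-SR16 and the ASDAS activity states. So are the continuous measures: Patient Global, spinal pain, CRP, BASMI and the other mobility measures, enthesitis and joint-count change, fatigue, JSEQ, WPAI-SpA, SF-36 MCS and domains, and QIDS. The NSAID rows differ: Table RHBW.6.5 gives them a Week 16 time point in the Period 3 population.

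At stake is how the maintenance evidence on these endpoints reads. No tested conclusion depends on it.

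**Working it through.** **Plan's own figure.** The documents state no dropout before Week 16 and no expected Week 52 result. The only stated performance figure is for Week 16: "this study will have approximately 96% power to test the superiority of ixekizumab Q2W to placebo for the ASAS40 at Week 16", with assumed rates of "27% for ixekizumab Q2W treatment group and 7% for placebo group". Exact enumeration of the two-sided Fisher test with 100 per arm at 0.05 gives 96.5%, so it reproduces. It concerns ASAS40 at Week 16 and does not bear on this point.

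**Responder measures (NRI, SAP 6.3.1).** Let d be the share of an ixekizumab arm not dosed in Period 3, and r the response rate at a Period 3 visit with all randomized patients in the denominator. Patients not dosed in Period 3 cannot count as responders at that visit, so both populations share one numerator:

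rate in Period 3 population = r / (1 − d)

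The relative inflation is 1/(1 − d) − 1, whatever r is. With d assumed to be 5% to 12%, and two purely illustrative values of r (the documents give none for an affected endpoint):

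| d (assumed) | 1/(1 − d) | r = 20% shows as | r = 40% shows as |
|---|---|---|---|
| 5% | 1/0.95 = 1.053 | 21.1% | 42.1% |
| 8% | 1/0.92 = 1.087 | 21.7% | 43.5% |
| 12% | 1/0.88 = 1.136 | 22.7% | 45.5% |

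Conversely, the display is flat when the Week 52 all-randomized rate equals the Week 16 rate times (1 − d). With d = 10%, 40 responders of 100 at Week 16 and 36 at Week 52 would show as 40/100 = 40% and 36/90 = 40%.

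Only losses before Period 3 dosing matter. Patients who stop after a Period 3 dose stay in the denominator as nonresponders.

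**Continuous measures (mBOCF, SAP 6.3.2).** Baseline is carried forward only for patients who stop because of an adverse event; for other reasons the last observation is carried. With both populations summarized under mBOCF:

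mean in Period 3 population − mean in ITT = d × (mean in stayers − mean in lost patients)

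Take d = 10% and a mean change of −2.5 in stayers (assumed; negative is improvement):

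- Lost patients at 0: ITT mean = 0.9 × (−2.5) + 0.1 × 0 = −2.25. The Period 3 population overstates improvement by 0.25.
- Lost patients at −2.5: ITT mean = −2.50. No shift.
- Lost patients at −3.0: ITT mean = 0.9 × (−2.5) + 0.1 × (−3.0) = −2.55. The Period 3 population understates improvement by 0.05.

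The direction therefore depends on how the lost patients fared. The estimate also changes in kind: for repeatedly measured continuous variables, the Period 2 method is MMRM without imputation (Protocol 9.4.2.2.1), while Period 3 has raw descriptive statistics.

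**The case against.** The strongest reply is that the plan already has the remedy where it matters most. Section 6.1.3 gives the all-randomized Week 0 to 52 summary for the primary endpoint, the major secondary endpoints and four further responder measures. Section 6.1.2 also follows Week 16 ASAS20 and ASAS40 responders and nonresponders through Period 3. This stands. A reader might infer that maintenance of ASAS40 or another key endpoint is overstated; the documents do not support that.

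The Period 3 population is also prespecified openly in Protocol 9.2.4 and 9.4.2.2.2, and the results are descriptive. This stands, and it limits the weight of the point.

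A reader might go further and say that a real loss of response is hidden. That is too strong. Section 6.1.2 reports numbers as well as percentages, and Section 6.6 reports disposition by initial randomized group. The all-randomized rate for a binary measure can be recovered as the reported count over the number randomized, or over the relevant baseline subset. The loss is obscured, and the reader has to do the division.

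Nor is there a general jump from Week 16 to Week 20. In the Schedule of Activities, Patient Global, spinal pain and CRP are collected at Week 20, and partial remission can be derived then. Mobility, enthesitis and joint counts next appear at Week 24; fatigue, JSEQ, SF-36, ASAS HI and QIDS at Week 36; and WPAI-SpA at Week 52.

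Finally, the absence of a Week 16 value in the Period 3 population is partly read from silence. Section 6.1.2 refers to all scheduled visits for continuous measures and starts Period 3 at the Week 16 injection. Outside the NSAID rows, however, no Week 16 display in that population is specified.

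None of this explains why the sponsor's like-for-like summary stops short of endpoints under the same objective.

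**Conclusion.** The point holds for other secondary and health-outcome endpoints outside the Section 6.1.3 list. For NRI responder measures the direction is certain whenever d is above zero and there are responders: the displayed Period 3 rate is inflated by 1/(1 − d), about 5% to 14% in relative terms for an assumed d of 5% to 12%. That range is an assumption, because the documents give no figure for d. For continuous measures the shift is d × (mean in stayers − mean in lost patients) and may be upward, zero or downward, so a general statement that they are overstated is not supported.

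Not affected are the primary endpoint, the major secondary endpoints assessed at Week 52, BASDAI50, ASDAS inactive disease, ASDAS clinically important and major improvement, and anterior uveitis. No hypothesis test or error rate is involved. This is a cheap improvement to descriptive reporting, worth making because these tables are the planned evidence on maintenance for these endpoints.

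**What to change.** In SAP 6.1.3 and Tables RHBW.6.1, 6.5 and 6.7, extend the Combined Periods 2 and 3 summary (ITT patients initially randomized to ixekizumab, NRI or mBOCF, all scheduled visits) to the remaining endpoints under the maintenance objective, at least to the responder measures. Base statements about maintenance on that summary.

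At the minimum, print the Week 16 value in the Extended Treatment Period Population beside the later visits, and label the series as conditional on entering Period 3.

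A paired Week 52 minus Week 16 change per regimen with a 95% CI is optional. Protocol 9.4.2.2.2 leaves room for within-group comparisons, but the denominator problem can be fixed without one.

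The cost is a few more descriptive tables from existing programs and datasets, with no new data.

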6.1.4. General Considerations for Analyses during the Post-Treatment Follow-Up Period (Period 4)

For the safety analyses during Period 4, baseline is defined as the last nonmissing assessment on or before entering Period 4, that is, on or before Week 52 (Visit 15), or ETV.

Safety data collected will be summarized using descriptive statistics.

Efficacy data collected during Period 4 will be summarized as described in Section 6.10.5.

6.1.5. Analysis Populations

The following major analysis populations will be used (additional analysis populations for specific analysis will be defined in the corresponding analysis section):

Intent-to-Treat Population (ITT Population): Unless otherwise specified, efficacy and health outcomes analyses for Period 2 will be conducted on the ITT Population, defined as all randomized patients, even if the patient does not take the assigned treatment, does not receive the correct treatment, or otherwise does not follow the protocol. Patients will be analyzed according to the treatment to which they were assigned.

Per-Protocol Set (PPS): In addition, the primary efficacy analysis will be repeated using the PPS, which is defined as all randomized patients who do not have a subset of important protocol deviations that impact the primary efficacy endpoint (Section 6.14). For example, patients who are not compliant with therapy during the double-blind period will be excluded from the PPS. Compliance with therapy is defined to be missing no more than 20% of expected doses, not missing 2 consecutive doses (all injections in an injection week are counted as 1 dose), and not have any occurrence of over-dosing (that is, took more injections at the same time point than specified in the protocol) during Period 2.

Patients will be analyzed according to the treatment to which they were assigned.

Safety Population: Safety analyses for Period 2 will be conducted on the Safety Population, defined as all randomized patients who received at least 1 dose of study treatment. Patients will be analyzed according to the treatment to which they were assigned in that period.

Extended Treatment Period Population: Efficacy, health outcomes, and safety analyses for Period 3 will be conducted on the Extended Treatment Period Population, defined as all patients who received at least 1 dose of ixekizumab treatment during Period 3.

All Ixekizumab Exposures Safety Population: Safety analyses for combined Blinded Treatment Dosing Period and Extended Treatment Period will be conducted on the All Ixekizumab Exposures Safety Population, defined as all patients who received at least 1 dose of ixekizumab during the study. For each patient, only periods in which ixekizumab is administered are included.

Follow-Up Population: Safety analyses for Period 4 will be conducted on the Follow-Up Population, defined as all randomized patients who received at least 1 dose of study treatment and have entered Period 4. Patients will be analyzed according to the treatment they received before entering the Follow-up Period. [Table RHBW.6.1](#) summarizes the major analysis purposes intended for each analysis population.

[Table RHBW.6.2](#) describes the treatment groups and the comparisons for each study period and analysis population.

Table RHBW.6.1. Major Analysis Purposes Intended for Each Analysis Population

	ITT Population	Per-Protocol Set	Safety Population	Extended Treatment Period Population	ITT Safety Population Who are Initially Randomized to Ixekizumab at Week 0	All Ixekizumab Exposures Safety Population	Follow-Up Population
Disposition	For Period 2			For Period 3			For Period 4
Baseline Characteristics ^a	For baseline			For baseline			
Treatment Compliance			For Period 2	For Period 3			
Concomitant Medication	For Period 2			For Period 3			
Protocol Deviation	For Period 2			For Period 3			
Exposure			For Period 2	For Period 3	For Combined Periods 2 and 3	For Periods 2 and 3, on ixekizumab treatment only	
Efficacy and Health Outcomes Analyses	For Period 2; For Period 4, only ASAS40	For ASAS40, ASAS20 in Period 2		For Period 3	For primary and major secondary objectives, and selective measures in Combined Periods 2 and 3		
Safety Analyses			For Period 2	For Period 3	For Combined Periods 2 and 3	For Periods 2 and 3, on ixekizumab treatment only	For Period 4
Subgroup Analyses on Efficacy Outcome	For Period 2						
Subgroup Analyses on Safety Outcome			For Period 2				

Abbreviations: ASAS = Assessment of Spondyloarthritis International Society; ITT = intent-to-treat.

^a including patient demographics and other baseline characteristics, historical illness, pre-existing conditions, prespecified medical history, previous therapy.

Table RHBW.6.2. Treatment Groups and Comparisons for Each Study Period and Analysis Population

Study Period	Analysis Population	Treatment Group	Abbreviation	Comparison
Blinded Treatment Dosing Period (Period 2)	Intent-to-Treat Population; Per Protocol Set; Safety Population	Placebo Ixekezumab 80 mg Q4W Ixekezumab 80 mg Q2W Total Ixekezumab Total Add the following treatment groups for analyses evaluating the impact of ixekizumab starting dose: Ixekezumab 80 mg Q4W/80 mg Starting Dose Ixekezumab 80 mg Q4W/160 mg Starting Dose Ixekezumab 80 mg Q2W/80 mg Starting Dose Ixekezumab 80 mg Q2W/160 mg Starting Dose Total Ixekezumab/80 mg Starting Dose Total Ixekezumab/160 mg Starting Dose	PBO IXE80Q4W IXE80Q2W Total IXE Total	IXE80Q4W vs. PBO IXE80Q2W vs. PBO Overall ^a IXE80Q4W/80S ^b vs. IXE80Q4W/160S ^b IXE80Q2W/80S ^b vs. IXE80Q2W/160S ^b Total IXE/80S ^b vs. Total IXE/160S ^b
Extended Treatment Period (Period 3)	Extended Treatment Period Population	Placebo/Ixekezumab 80 mg Q4W Placebo/Ixekezumab 80 mg Q2W Ixekezumab 80 mg Q4W/Ixekezumab 80 mg Q4W Ixekezumab 80 mg Q2W/Ixekezumab 80 mg Q2W Placebo/Ixekezumab 80 mg Ixekezumab 80 mg/Ixekezumab 80 mg Total	PBO/IXE80Q4W PBO/IXE80Q2W IXE80Q4W/IXE80Q4W IXE80Q2W/IXE80Q2W PBO/IXE IXE/IXE Total	No Between-Group or Overall Comparisons
Combined Periods 2 and 3	Intent-to-Treat Population Who are Initially Randomized to Ixekezumab	Ixekezumab 80 mg Q4W Ixekezumab 80 mg Q2W Total Ixekezumab	IXE80Q4W IXE80Q2W Total IXE	No Between-Group or Overall Comparisons
Combined Periods 2 and 3	Safety Population Who are Initially Randomized to Ixekezumab	Ixekezumab 80 mg Q4W Ixekezumab 80 mg Q2W Total Ixekezumab	IXE80Q4W IXE80Q2W Total IXE	No Between-Group or Overall Comparisons

Treatment Groups and Comparisons for Each Study Period and Analysis Population

Combined Periods 2 and 3 (on Ixekizumab treatment only)	All Ixekizumab Exposures Safety Population ^e	Ixekizumab 80 mg Q4W Ixekizumab 80 mg Q2W Total Ixekizumab	IXE80Q4W IXE80Q2W Total IXE	No Between-Group or Overall Comparisons
Post-Treatment Follow-up Period (Period 4) ^d	Follow-Up Population	Placebo Ixekizumab 80 mg Q4W Ixekizumab 80 mg Q2W Total Ixekizumab Total	PBO IXE80Q4W IXE80Q2W Total IXE Total	No Between-Group or Overall Comparisons

Abbreviations: IXE80Q2W = ixekizumab 80 mg every 2 weeks; IXE80Q4W = ixekizumab 80 mg every 4 weeks; IXE = Ixekizumab including IXE80Q2W and IXE80Q4W; PBO = placebo.

- a Overall comparison will be conducted for demographics, historical illness, medical history, pre-existing condition, and previous therapy. The between-group comparisons and the overall comparison will be conducted for concomitant therapy, compliance, disposition, and safety.
- b S=Starting does; differences between starting dose groups and 95% CI will be provided.
- c For Extended Treatment Period Population, ‘Total Ixekizumab 80 mg Q4W’ is a pooled group of ‘Placebo/Ixekizumab 80 mg Q4W’, and ‘Ixekizumab 80 mg Q4W/Ixekizumab 80 mg Q4W’; similarly, ‘Total Ixekizumab 80 mg Q2W’ is a pooled group of ‘Placebo/Ixekizumab 80 mg Q2W’, and ‘Ixekizumab 80 mg Q2W/Ixekizumab 80 mg Q2W’.
- d Treatment group refers to the treatment regimen that the patient received before entering Period 4.
- e Defined as all patients who received at least 1 dose of ixekizumab during the study

